Additionally, there is not a systematic emergency medical transport system available for provision of medical care and resuscitation during transport. Enteral-based resuscitation with substances like the WHO Oral Rehydration Solution (ORS) is recommended by burn experts and the professional burn societies when resources and access to intravenous fluid resuscitation are not available in resource-constrained settings such as rural areas, low- and middle-income countries, and military battlefield scenarios. Studies have previously demonstrated the efficacy and safety of enteral-based resuscitation in controlled, high-resource settings, however there have not been real-world effectiveness trials in austere settings. Therefore, we seek to ultimately address the problem of pre-hospital and pre-burn center admission resuscitation by studying the feasibility and effectiveness of enteral resuscitation with Oral Rehydration Solution (ORS) in preventing burn shock. An attachment has been provided with a more detailed literature review of enteral-based resuscitation research for burn injuries with references for further information on this topic (**Appendix**).

Additionally, enteral-based resuscitation with ORS has been widely applied in other pathologies resulting in massive dehydration and ultimate death, such as diarrheal illnesses. ORS is a mixture of salts and sugar dissolved in water, created and modified in the 1940's-1970s. Use of ORS demonstrated a significant reduction in mortality from dehydration and multisystem organ failure during the cholera epidemic, and is used around the world in the setting of diarrheal illnesses. Given similar principles of rapid dehydration in the setting of burn injuries as well as the multiple studies demonstrating efficacy and safety of enteral-based resuscitation for moderate sized burn injuries, we plan to study the effectiveness of enteral resuscitation with ORS for burn resuscitation in Nepal.

The current project seeks to address gaps in our understanding of logistical and cultural barriers to protocolized enteral-based resuscitation (either drinking by mouth or via a nasogastric tube), and feasibility of protocolized intravenous resuscitation. The current project will also retrospectively review epidemiologic registry data, perform geospatial analysis and inform anticipated larger studies of multi-site enteral resuscitation trials.

7. Objectives

Many patients in low- and middle-income countries (LMICs) do not receive appropriate fluid resuscitation after sustaining a potentially survivable burn injury due to lack of resources or expertise. This population encompasses 90% of the 9 million people burned annually around the globe. Given current safety and efficacy data, burn care experts recommend enteral resuscitation (i.e., oral rehydration solution administered by mouth or nasal-enteric tube) instead of solely intravenous resuscitation, particularly when resources for acute burn care are scarce. However, there have been no studies to determine the real-world effectiveness and feasibility, acceptability,

facilitators and barriers for sustainability of enteral resuscitation for burn injuries in austere settings. In our initial studies, we have demonstrated feasibility of implementing the enteral resuscitation bundle, as well as feasibility of research study.

8. Trial Design

The study design is a mixed-methods implementation-effectiveness trial consisting of randomization of eligible participants into protocol-based enteral-based resuscitation vs protocol-based intravenous resuscitation (standard of care) arms to assess feasibility of protocol and randomization. The qualitative component entails semi-structured focus group interviews for involved healthcare providers assessing compliance, acceptability, feasibility, facilitators and barriers to sustainability of interventions.

9. Study Setting

The study will take place at the Nepal Cleft and Burn Center at Kirtipur Hospital (pfect-NEPAL) in Kirtipur, Nepal which is the major tertiary burn care center in Nepal.

Nepal Cleft and Burn Center is an ideal to study burn resuscitation in austere settings given a very high incidence of serious burn injuries, frequent delays in resuscitation, and critically limited resources. By studying an enteral-based resuscitation bundle in this population, we can assess feasibility of the bundle within a realistic resource-limited context where a need exists.

10. Eligibility Criteria

Intervention:

Inclusion Criteria

Male or female; adults aged ≥ 18 years who present with moderate-sized burn injuries [15 – 40% total body surface areas (TBSA)] to the Nepal Cleft and Burn Center within 24 hours of injury.

Exclusion Criteria

Patients with electrical and chemical burns will be excluded, as will those with serious inhalation injury requiring treatment to maintain oxygen saturation. Patients in overt shock (defined as serum lactate >2.5 , or hypotension and altered mental status), Pregnant patients, psychiatrically unstable patients will be excluded.

Patients with oropharyngeal defects and/or previously known diagnoses leading to high risk of aspiration, and/or precluding safe nasal-enteric access will be excluded. Patients with history of chronic nausea and/or vomiting, including those with a diagnosis of gastroparesis due to diabetes mellitus will be excluded.

Patients with a Baux score of over 100 (age + TBSA), patients with declared palliative intent on admission, and patients for whom clinicians have high level of clinical concern based on clinical judgement will also be excluded.

Qualitative Component:

Inclusion Criteria

Healthcare workers (physicians, nurses, nursing assistants) who are anticipated to or have provided care to eligible patients in the enteral resuscitation arm of the study.

[figure not shown]
Exclusion Criteria

Exclusion criteria include co-PIs and co-investigators in this study to avoid bias.

11. Intervention

Please see schematic below for Intervention workflow. Specific goal-directed resuscitation protocols for IV fluid resuscitation and Enteral-based resuscitation in **Appendix** including details regarding modifications to allocated interventions based on response, patient request and improving/worsening disease.

Intervention Workflow Overview

General Resuscitation Protocol for Intravenous and Enteral-based Resuscitation

Resuscitation Timeline	Fluid Protocol	Clinical Assessment	Laboratory Assessment*	Additional Interventions
Hour 1	See Appendices A and B	Measure and record vital signs every two hours or more frequently as needed. (Temperature, blood pressure, heart rate, respirations, oxygen saturation), urine output, physical signs of overt shock	CBC, BMP, Lactate, PT/PTT/INR (15 mL)	Additional interventions such as colloid or blood product transfusion, vasoactive agents, escharotomy/ faschiotomy, intubation as deemed necessary by clinical care team will be noted throughout this time period.
Hours 2-7				
Hour 8	Administer Lactated Ringer's (LR) or Oral Rehydration Solution + LR according to calculated Parkland formula**		CBC, BMP, Lactate (10 mL)	
Hours 9-15				
Hour 16	Add or subtract fluid volume by every 2 hours based on urine output goal of at least 0.5 mL/kg/hr.		CBC, BMP, Lactate (10 mL)	
Hours 16+	IV Metoclopramide to be administered if GI symptoms such as bloating, nausea, discomfort, vomiting.		CBC, BMP, Lactate every 8 hours, and PT/PTT/INR every 24 hours until resuscitation complete.	

* CBC=Complete blood count; BMP=Basic metabolic panel; PT=Prothrombin time; PTT=Partial Thromboplastin time; INR=international normalized ratio

**Parkland formula= $4\text{cc} * \% \text{ Total Body Surface Area burned(TBSA)} * \text{weight(kg)} = 24 \text{ hour fluid volume}$
Total resuscitation volume divided by 2, then divided by 8 to determine the starting resuscitation volume.

12. Outcomes

Goals

The overarching goals are to understand challenges and facilitators of enteral-based resuscitation and understand the effectiveness of the technique compared to standard of care (intravenous resuscitation).

Specific Aim 1: Determine the frequency of adherence to the enteral-based and IV fluid resuscitation protocols, and determine frequency of successful resuscitation.

Hypothesis 1: With goal-directed resuscitation, the primary outcomes of goal average urine output and successful resuscitation will be achieved in the majority of patients (over 50%). Protocol adherence will be at least 50%.

Specific Aim 2: Describe the challenges and facilitators to enteral and IV resuscitation protocol acceptance, implementation, compliance and sustainability.

Hypothesis 2: Enteral resuscitation will have logistical advantages over IV resuscitation, reduce delays in the initiation of resuscitation, have fewer interruptions, and will be easier to implement.

Primary endpoints

For the quantitative aspect, study variables will include measures of implementation and adherence to the enteral resuscitation protocol with variables such as: percent of resuscitation conducted enterally, proportion of protocol laboratory and clinical assessments completed, completeness of bedside documentation, number of inappropriate adjustments of resuscitation fluid rates based on urine output.

For the qualitative aspect, study variables and themes will be assessed to include the acceptability of the intervention for healthcare workers, acceptability of the intervention for patients, burden of the intervention and protocol for healthcare workers, acceptance of the protocol, perceived knowledge gaps, comfort level with the intervention protocol, concerns with the intervention, favored aspects of the intervention. These study variables will be ascertained from the interview guides, developed using the Consolidated Frameworks for Implementation Research (CFIR).

13. Participant Timeline

Patient screening and enrollment will occur after patient assessment in the Emergency Department at Kirtipur Hospital. After consent and enrollment, randomization to the intervention bundle will occur within the ED.

Treatment will commence per intervention assignment. The patient's clinical status and specific clinical metrics will be assessed every 2 hours during the acute resuscitation period, with laboratory marker measured every 8 hours. The acute resuscitation period typically lasts 24-72 hours.

Within 2 days of completing resuscitation, each patient will undergo a 10-15 minute semi-structured interview with a research assistant regarding their experience and opinion of the resuscitation bundle.

Patients data will be followed for the duration of their inpatient hospitalization in order to track hospital course, and outcomes such as survival and disposition. All communication with the patient and their families will be in person. If the patient and their family opt to do so, they can be contacted after the conclusion of the study with notification of the study results.

14. Sample Size

We would like to update the target patient enrollment to 240 patients. The sample size calculations are demonstrated below, with a necessary sample size of 212 and a 14% increase in target enrollment to account for missing data/dropouts. We assumed an absolute difference in the prevalence of the primary outcome (24-hour UOP within target range) of 20% between the exposed and unexposed, based off of available literature. This is non-probability-based convenience sampling of patients who present with acute burn injuries to Kirtipur Hospital.

Alpha: 0.05 (95% Confidence Level)

Power: 80%

Ratio of unexposed/exposed in sample: 1

Percent of unexposed with outcome: 35%

Percent of exposed with outcome:	Prevalence Difference vs. unexposed	Odds Ratio	Necessary Sample Size
55	20%	2.3	212

15. Recruitment

Patients will be screened by research study team members for eligibility in the Emergency Department at Kirtipur Hospital. All recruitment and screening will occur in the Emergency Department and inpatient setting on admission. No outside recruitment will occur. The study will aim to enroll over the winter season, as this is the timeframe with the highest incidence rate of burn injuries in Nepal.

Methods

16. Allocation

The patient treatment allocation sequence will be generated using the sealed envelope technique. The sealed envelopes for each sequentially numbered enrolled patient (e.g. Patient 1, Patient 2, Patient 3, etc) will contain a pre-assigned intervention arm that will be unknown to the research team prior to each patient's enrollment. Each sealed envelope will only be opened after patient enrollment is complete to reveal patient intervention arm allocation.

17. Blinding

This study is not blinded to the patients or providers.

18. Data Collection Methods

Intervention:

In order to ensure a contextually appropriate intervention and increase engagement, data collection tools have been adapted from the validated Joint Trauma System Burn Care Clinical Practice Guideline 12 (JTS Burn Care CPG 12) burn worksheet and resuscitation flowsheet with feedback from stakeholders at the Nepal Cleft and Burn Center. Please see attached documents (Resuscitation Flowchart and Documentation Chart) for the latest versions developed by the research and clinician team, to be further adapted for ease of use as needed.

Clinical data pertaining to the resuscitation interventions will be collected and documented by the bedside nurses and clinicians on the adapted Documentation Chart, with documentation of i) brief history and physical exam ii) two-hourly assessments of vitals, intake, output, and symptoms and iii) 8 hourly laboratory test results. This data will subsequently be transcribed into a secure electronic format by research assistants utilizing the RedCAP data collection system.

Post-resuscitation patient interview answers will be recorded on the RedCAP data collection system.

Qualitative Component:

Data collection tools include focus group interview guide which will serve to guide the semi-structured 1-hour discussions pre-enrollment, at 50% enrollment and after completion of enrollment with groups of doctors and nurses caring for the patients enrolled in the study. The

focus group interview guides are adapted from the Consolidated Frameworks for Implementation Research (CFIR), a validated and widely used tool in Implementation Science research.

The focus group interviews will be audio-recorded, with audio files immediately transferred to a secure, password-protected data storage system. These audio files will subsequently transcribed and translated for thematic analysis.

19. Data Management

Personal patient information such as the collected demographic data and patient clinical outcomes data will be collected into a password protected, HIPPA compliant data storage system (REDCap®). The REDCap electronic data collection form will have built-in validation measures to ensure data quality and mitigate missing data (i.e; required entries, range checks, multiple choice single answer questions). When the data are downloaded for analysis, they will be downloaded in a de-identified manner. The physical charts with patient information such as the Documentation Chart will remain within the patient's medical record as a component of their records.

The majority of the patient in-depth interview guide will be adapted from validated tools to assess patient socioeconomic status, to assess household fire risk and safety, and cookstove safety. The interview will be audio-recorded, on two devices to ensure capture of the data in case of technical issues with the recording devices. The audio-files will be immediately transferred from the recording devices to a secure, password protected electronic data storage platform via a password protected device that is kept in a secure, locked location when not in use by the research assistants. The audio-files will be transcribed and translated, and a coded system will be utilized to de-identify the data. All qualitative analysis will take place using de-identified data. The datafiles will be retained for a minimum of 3-5 years after conclusion of the study per regulatory requirements.

Data downloaded for analysis will be de-identified. Data will be maintained in an electronic data storage platform (OneDrive for Business). The data will be managed by the University of Washington study team members. The co-Principle Investigators and co-Investigators (listed above) will have access to the final, de-identified data for purposes of data analysis. The Data Safety Management Board will also have access to the patient data for patient safety monitoring purposes.

20. Statistical Methods

We will perform descriptive and comparative statistics for both qualitative and quantitative implementation metrics. Qualitative analysis of the patient and focus group interviews will use a template analysis approach to code and organize data for cross-case analysis of patterns of challenges and facilitators for each component of the resuscitation bundle.

21. Data Monitoring

The research team will conduct weekly virtual meetings (increasing frequency of meetings as needed) to discuss progress and relevant issues. We will measure against our internal timelines of progress, including enrolling 10 patients per month after enrollment begins. [name], study PI, and [name], study co-I, along with trained research assistants will be present for day to day monitoring, questions and problem solving. [name], U.S.- based PI will monitor all data submitted to RedCap for issues or patient safety concerns. [name], study co-I

and Assistant Professor of Surgery at University of Washington, will serve as a mentor for supervision and guidance on conducting the study.

Additionally, a Data Monitoring and Safety Board will be developed to monitor patient adverse events (AE) and serious adverse events (SAE). This is described below in section 22.

22. Harms

All patient clinical Adverse Events (AE) and Serious Adverse Events (SAE) will be monitored by study PIs. Furthermore, solicited or spontaneously reported adverse events will be reported to the study PIs. These will be investigated internally, in addition to reporting to the DSMB. All SAE will be reported to the DSMB within 1 working day of occurrence. All other AE and solicited or reported AE will be provided to the DSMB by study PI or Research Coordinator on a weekly basis.

Definitions:

Adverse Events (AE): are defined as those characterized as temporary in nature, mild symptomatology and no risk of long-term impact on morbidity and mortality, i.e. nausea/vomiting

Serious Adverse Event (SAE): those with risk of long-term impact on morbidity and mortality such as aspiration events, kidney injury requiring renal replacement therapy, and death.

Patients who experience serious adverse events attributed as a consequence of participation in the study may have costs of additional care (such as ventilation needs, renal replacement therapy needs) covered by the study.

23. Auditing

Trial conduct will be audited by the DSMB when it convenes to review serious adverse events. DSMB members will have access to the collected data to review. There will not be planned in-person audits unless requested by the DSMB members. The DSMB will be independent of study members.

Ethics and dissemination

24. Research Ethics Approval

The study is undergoing ongoing human subjects ethical review by the University of Washington Institutional Review Board and the Nepal National Health Research Council. Institutional approval has been obtained from the phect-NEPAL institutional ethical review board. The study team will work with the above ethical review boards to complete modifications as requested and amend the protocol.

25. Protocol Amendments

Important protocol modifications including changes to eligibility criteria, outcomes and analyses will be communicated to associated Institutional Review Boards (IRB) and trial registries.

Outcomes and analyses will be presented to local and international burn care providers, and manuscripts reflecting the trial outcomes and analyses will be published in local and international journals.

26. Consent or assent

Intervention

Informed consent will be obtained from all patients and/or their authorized surrogate by our research team's trained research assistants after the patient has been identified as eligible for the study on screening and agrees to participate in the study. The consent form will be available in English and Nepali. Please see consent form (Appendix).

For patients who are functionally illiterate, consent will be obtained after understanding and agreement to participate in the study is confirmed by a witness. The patient to be enrolled will provide fingerprint signature, and the witness will sign in the designated area.

Qualitative Component:

Informed consent will be obtained from all participants (doctors, nurses) who participate in the Focus Group Interviews. The consent form will be available in English and Nepali.

All study participants including those from the Intervention and the Qualitative Component will be made aware of their ability to withdraw from the study at any time, and will be instructed in the channels to do so.

27. Confidentiality

Personal patient data will be collected and stored into a password protected, HIPPA compliant data storage system (REDCap®). If downloaded for analysis, the dataset will be downloaded in a de-identified manner in order to protect patient confidentiality during and after the trial. The DSMB and the PIs and Research Coordinator will have access to patient data with identifiers for patient safety monitoring purposes.

28. Declaration of Interests

The PIs and Co-Is have no financial or competing interests to declare for the trial of the study site at the Nepal Cleft and Burn Center.

29. Access to Data

Each of the study PI and Co-I ([name], [name], [name]), the Research Coordinator, Data analysts, and the DSMB members will have access to the final trial dataset.

30. Ancillary and Post-Trial care

The enrolled patients will continue to receive care per the standard of care after conclusion of the resuscitation portion of the study. The costs incurred for the remainder of standard of care (including operative management) will not be covered by the study.

31. Dissemination Policy

After conclusion of the study and data analysis, results will be presented to the healthcare providers at the study institution (Nepal Cleft and Burn Center at Kirtipur Hospital). Additionally, at the time of enrollment, patients will be asked if they would like to be contact in the future regarding study results. The patients who agree will also receive information regarding the results of the study.

The study analysis and results will be developed into manuscripts for publication as appropriate. The team will target both local and international journals, as well as local and international burn care conferences. PIs and Co-PIs, as well as research team members who contribute to the

study implementation and manuscript development will be included as co-authors in publications. The results are planned to be disseminated within 1 year of study conclusion.

Appendices

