Appendix B: Resuscitation Protocol Flowsheets and Documentation Chart

Enhanced Adult Burn Fluid Resuscitation Protocol for Intravenous Fluid Only Resuscitation

Use for Adults ≥ 18 years, not for pediatric patients, electrical/chemical burn patients or patients with suspected inhalation injury

- Baseline fluid calculation per Parkland Formula ($4\text{cc} \times \% \text{ TBSA} \times \text{weight (kg)} = 24\text{-hour fluid volume}$)
- Vital signs including Heart Rate (HR), Blood Pressure (BP), O₂ saturation and Urine Output (UO) should be tracked every 1 to 2 hours, with fluid rate adjusted accordingly
- **Target Urine Output = 0.5 mL/kg/hr; HR < 120 bpm; Systolic BP >90 mmHg**
- If hypotensive with EITHER Intravenous or enteral-based resuscitation, give bolus of 10cc/kg IV fluids. Consider vasopressor or colloid augmentation.
- For all calculated hourly resuscitation volumes, please round to the nearest 10 (i.e., 74 =70ml, 76=80mL)

[figure not shown]

Adult Burn Fluid Resuscitation Protocol for Enteral-based Resuscitation

Use for Adults ≥ 18 years, not for pediatric patients, electrical/chemical burn patients or patients with suspected inhalation injury

- Vital signs including Heart Rate (HR), Blood Pressure (BP), O₂ saturation and Urine Output (UO) should be tracked every 1 to 2 hours, with fluid rate adjusted accordingly
- Goal: UO=0.5 mL/kg/hr, HR < 120, Systolic BP >90
- If hypotensive with EITHER resuscitation type, give bolus of 10cc/kg IV fluids. Consider vasopressor or colloid augmentation.
- ORS can be administered by drinking or administering the calculated volume via NGT every hour
- For all calculated hourly resuscitation volumes, please round to the nearest 10 (ie 76=80mL)

Abbreviations: IV= Intravenous, RL= Ringer's Lactate, ORS= Oral Rehydration Solution, NGT= Nasogastric Tube

Today's Date: / / 2021			Date and Time of Injury: / / 2021; : AM/PM			InPatient No:							
Name		Admission Wt. (kg)	%TBSA (Do not include superficial 1 st degree burn)			Burn Mechanism							
Parkland Formula: Total Resuscitation Volume: _____ % X _____ kg X 4ml = _____ in 24 hours (TBSA) (pt. weight)						First 8 hours (use 1/2 of total volume) _____ ÷ 8 hrs. Starting Hourly Fluids = _____ ml/hour			Starting 2 Hourly I.V Fluid _____ ml				

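### Section 10 excludes only serious, treated inhalation injury, but both Appendix B arm protocols rule out any suspected inhalation injury

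*Combined protocol and SAP*

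**What the plan says.** Section 10 (Exclusion Criteria) removes, on this ground, "those with serious inhalation injury requiring treatment to maintain oxygen saturation". The same section ends its list with a catch-all: "patients for whom clinicians have high level of clinical concern based on clinical judgement will also be excluded".

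Section 11 locates the interventions elsewhere: "Specific goal-directed resuscitation protocols for IV fluid resuscitation and Enteral-based resuscitation in" the Appendix. The sheets are in Appendix B, one for intravenous-only and one for enteral-based resuscitation. Under each title the same line limits use to adults and adds "not for pediatric patients, electrical/chemical burn patients or patients with suspected inhalation injury".

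On the order of events, Section 13 states: "Patient screening and enrollment will occur after patient assessment in the Emergency Department at Kirtipur Hospital". Section 16 states: "Each sealed envelope will only be opened after patient enrollment is complete to reveal patient intervention arm allocation". Section 13 then adds: "Treatment will commence per intervention assignment".

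**The concern.** The two rules describe different populations. Section 10 lets in patients with suspected or milder inhalation injury as long as they need no treatment to maintain saturation. The Appendix B headers shut out anyone in whom inhalation injury is suspected, with no threshold of severity or treatment.

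If the mismatch is first noticed at the bedside, the patient has already been enrolled and allocated, and neither arm has a sheet that claims to cover that patient. Staff must then either follow a sheet outside its stated scope, which is a safety question, or depart from it. The visible text does not say how a departure of this kind would be classed. That matters because adherence to both protocols is Specific Aim 1, and Hypothesis 1 expects it to be at least 50%.

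There is also a question of who was studied. A screener working from Section 10 and one working from the sheet could enrol different patients, and a reader of the results could not tell which rule had been applied.

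**Working it through.** The plan gives no figure on this point, so the check compares the texts.

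**Step 1. Is the header part of the trial intervention?** Section 11 refers to the Appendix for the arm-specific protocols, and those protocols are the two sheets in Appendix B. The header line therefore sits on the interventions themselves.

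**Step 2. Compare each header restriction with Section 10.**

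| Header restriction (both sheets) | Section 10 | Agreement |
|---|---|---|
| Adults aged 18 or over, not children | Adults aged 18 or over | Yes |
| Not electrical or chemical burns | Electrical and chemical burns excluded | Yes |
| Not suspected inhalation injury | Only serious inhalation injury needing treatment to maintain saturation is excluded | No |

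So 1 of 3 restrictions differs, and it appears on 2 of 2 sheets. Because the other two match, the header reads as a restatement of eligibility with one item out of line.

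**Step 3. How do the inhalation rules differ?** They differ in certainty (suspected against established), in severity (any against serious) and in condition (none against a need for treatment). The visible text defines neither serious nor suspected inhalation injury.

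**Step 4. Which patients fall between the rules?** Take a patient who meets every other criterion, has suspected inhalation injury and needs no treatment to maintain saturation.
- Section 10 inhalation criterion: not excluded.
- Section 10 clinical-concern clause: excluded only if a clinician chooses to invoke it.
- Appendix B, intravenous sheet: outside its stated scope.
- Appendix B, enteral sheet: outside its stated scope.

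Unless the discretionary clause is used, the patient can be randomised, and neither possible allocation has a sheet that says it applies.

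**Step 5. Does anything visible settle precedence?** No. Section 18 allows the data collection tools to be adapted further for ease of use, but it does not rank them against Section 10. The workflow and flowsheet figures are not shown and could not be checked.

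**Step 6. Could the affected patients be counted afterwards?** The visible chart in Appendix B has fields for burn mechanism, %TBSA and oxygen saturation, and none for inhalation injury. Section 18 provides for "documentation of i) brief history and physical exam ii) two-hourly assessments of vitals, intake, output, and symptoms", so the information might exist as free text, which is harder to count. The REDCap form is not among the documents, so a structured field there cannot be ruled out.

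**The case against.** The strongest reply is that the two texts do different jobs. Section 10 sets eligibility, while the header is a usage note on a bedside sheet, and no passage makes it an enrolment criterion. The tools were adapted from an outside burn worksheet and flowsheet, the chart is pre-printed with the year 2021, and Section 7 refers to earlier studies by the team. The line may simply have been carried over. That is plausible, but it is an inference, and staff holding the sheet have no way to know it.

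There are also safeguards. Emergency department assessment comes before enrolment, so a clinician can use the clinical-concern clause in time. Once treatment starts, Appendix B calls for oxygen saturation every 1 to 2 hours, and the Section 11 table leaves intubation to the care team. These narrow the practical gap. They do not make the rules agree, and a discretionary clause may be applied differently by different clinicians.

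The figures that are not shown might address inhalation injury. That limit stands, although both conflicting rules are in visible text.

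The point about adherence carries weight. None of the measures listed in Section 12 scores whether a patient was within a sheet's scope, and a patient treated as assigned would score normally on them. The list is open-ended, so an effect on measured adherence is possible, but the documents do not show one.

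Finally, opening the envelope after enrolment is ordinary allocation concealment and is not a fault. It matters only because it makes screening the last point at which the conflict can be settled without affecting an allocated patient.

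**Conclusion.** The contradiction holds as written. A patient can satisfy Section 10 and be randomised between two protocols that both, by their own wording, are not for that patient. It should be corrected.

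Its size is unknown and may be zero: the documents give no frequency of suspected inhalation injury, and staff may already apply the stricter wording at screening. No effect on power or accrual is claimed. Both arms carry the same line, so the conflict does not by itself favour either. The consequences are a safety question about using a sheet outside its scope, an unclear eligible population, and a possible but undemonstrated effect on measured adherence.

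The conclusion rests on the visible text and assumes that the missing figures do not state which rule prevails. Which clinical rule is right is outside this review.

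**What to change.** Reconcile Section 10 with the two Appendix B headers so that all three use the same inhalation-injury wording, and apply that wording at screening before the envelope is opened. The clinical leads should decide which wording applies.

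As an optional addition, record suspected inhalation injury (yes/no) at screening, unless the REDCap form already does so. This would show the share of patients affected.

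The cost is one amendment, to Section 10 or to the two headers, plus one screening field if it is adopted. If eligibility is narrowed, accrual may be somewhat slower, by an amount the documents do not allow anyone to estimate. If staff already apply the header wording at screening, nothing is lost.
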